### 4. STUDY DESIGN

### 4.1. Overall Design

This is a Phase 1, open-label, single-dose, randomized 4-crossover periods and 1-fixed period design in a single cohort of approximately 16 healthy male or female participants .

The study will consist of 5 treatments as shown below:

- 1. Treatment A: Single oral dose of etrasimod 2 mg clinical IR tablet under fasted conditions (Reference)
- 2. Treatment B: Single oral dose of etrasimod 2 mg mini tablets mixed with applesauce under fasted conditions (Test 1)
- 3. Treatment C: Single oral dose of etrasimod 2 mg mini tablets mixed with chocolate pudding under fasted conditions (Test 2)
- 4. Treatment D: Single oral dose of etrasimod 2 mg mini tablets mixed with water under fasted conditions (Test 3)
- 5. Treatment E: Single oral dose of etrasimod 2 mg mini tablets mixed with yogurt under fasted conditions (Test 4)

Sixteen participants will be enrolled in Period 1 for a total of 12 evaluable participants to complete study. Participants will be randomly assigned to 1 of the 4 sequences shown in Table 2 in which participants are randomized in crossover design to receive Treatments A to D in Periods 1 to 4 with Treatment E being fixed in Period 5. Participants will be discharged on Day 9 of Period 5, following completion of all assessments. Each treatment is 9 days that includes dosing, PK sampling and an extra day to minimize any residual etrasimod concentrations prior to start of the next treatment. The total planned duration of participation from the screening visit to the last follow-up phone call, is approximately 14 weeks.

Treatment sequence (n=4 per sequence)	Period 1	Period 2	Period 3	Period 4	Period 5 (fixed)
1	А	В	С	D	Е
2	В	D	А	С	Е
3	С	А	D	В	Е
4	D	С	В	А	Е

 Table 2.
 Treatment Sequence

Since etrasimod has a half-life approximately 30 hours, there will be a 9-day washout between each dose.

Blood samples for PK analysis will be collected predose and at 1, 2, 4, 6, 8, 12, 24, 48, 72, 96, 120, 144 and 168 hours postdose (SoA). Capillary blood samples (using micro sampling Tasso device) will be collected at predose and at 1, 2, 4, 6, 8, 12 and 24 hours postdose (SoA) for PK assessments (Treatment A). Micro PK sampling occurs after PK blood sampling, and taken from the other arm.

A palatability assessment will be conducted during which a palatability assessment questionnaire will be completed for the sprinkled mini tablets in every period, with 1 minute (immediately after dosing), before administered the water up to a total volume of 240 mL, and at 5 minutes, 10 minutes, 20 minutes after dosing is fully completed. Additionally, participants will be asked to not verbalize their responses and not discuss palatability with other participants until after they have filled out the responses in the questionnaire.

Participants will participate in the study up to approximately 3.5 months, with the inclusion of the screening and follow-up period. Participants will be screened within 28 days of the first dose of study intervention and if all entry criteria are fulfilled, the participants will report to the CRU on the day prior to Day 1 dosing (Day -1). On Day 1 of each period, participants will receive a single dose of study intervention. Administration of etrasimod will be oral via dosing of clinical IR tablet 2 mg or mini tablets 2 mg (as  $16 \times 0.125$  mg) with water or on soft foods as per dosing instructions. Participants will be fasted for at least 10 hours predosing and 4 hours postdosing.

Participants will be confined in the CRU for a total of at least 45 days and discharged at the discretion of the investigator. A follow-up phone call will be made at least 28 calendar days and up to 35 calendar days after the last administration of the study intervention to capture any potential AEs and confirm appropriate contraceptive usage.

Tolerability and safety will be assessed for all treatments by monitoring AEs. Participants who withdraw from the study or whose PK samples are determined to be non-analyzable may be replaced at the discretion of the of the investigator upon consultation with the sponsor.

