# **3. OBJECTIVES AND ENDPOINTS**

Objectives	Endpoints
Primary:	Primary:

 
To estimate the rBA of etrasimod 2 mg mini tablets mixed with water compared to etrasimod 2 mg clinical IR tablets under fasted conditions
 
To estimate the rBA of the etrasimod 2 mg mini tablets mixed with applesauce compared to the etrasimod 2 mg clinical IR tablets under fasted conditions
 
To estimate the rBA of the etrasimod 2 mg mini tablets mixed with chocolate pudding compared to the etrasimod 2 mg clinical IR tablets under fasted conditions
 
To estimate the rBA of the etrasimod 2 mg mini tablets mixed with chocolate pudding compared to the etrasimod 2 mg clinical IR tablets under fasted conditions
 
To estimate the rBA of the etrasimod 2 mg mini tablets mixed with yogurt compared to the etrasimod 2 mg clinical IR tablets under fasted conditions
 
	• Plasma AUC last , AUC inf and C max of etrasimod
Secondary:	Secondary:
• To evaluate the safety and tolerability of etrasimod in healthy participants	• Assessment of first dose HR reduction, TEAEs, clinical laboratory abnormalities, vital signs, PEs, and 12-lead ECGs
• To assess the palatability of etrasimod mini tablets mixed with water/applesauce/chocolate pudding/yogurt	• Assessment of palatability via questionnaire: mouth feel, bitterness, tongue/mouth burns, throat burn, and overall liking
Tertiary/Exploratory:	Tertiary/Exploratory:
• To characterize the PK parameters of etrasimod 2 mg mini tablets mixed with water or soft foods (applesauce, chocolate pudding, or yogurt) compared to etrasimod 2 mg clinical IR tablet	
 
Plasma etrasimod: t1/2, CL/F, Vz/F and Tmax of etrasimod
 

• To validate the PK measurement of etrasimod in capillary blood sample collected using micro sampling device against the PK measurement of etrasimod in venous blood samples.	• Plasma concentration of etrasimod obtained via micro sampling compared to venous sampling

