### 6.1.1. Administration

On Day 1 of each period, following an overnight fast of at least 10 hours, participants will receive study intervention at approximately 0800 hours (plus or minus 2 hours). Investigator site personnel will administer study intervention during each period.

Etrasimod clinical IR tablets will be administered with ambient temperature water to a total volume of approximately 240 mL.

Etrasimod mini tablets will be administered mixed with 5 mL of either applesauce, chocolate pudding, yogurt or water followed by approximately 235 mL of ambient temperature water or by 5 ml rinsing if dispersion in water followed by 230 ml water. See IPM for detailed instructions on preparation and administration of study intervention.

Participants will swallow the clinical IR tablets whole and mini tablets mixed with applesauce, chocolate pudding, yogurt, or water, and will not manipulate or chew the study intervention prior to swallowing.

In order to standardize the conditions on PK sampling days, all participants will be required to refrain from lying down (except when required for ECG measurements), eating, and drinking beverages other than water during the first 4 hours after dosing.

Administration of study intervention(s) will be performed by an appropriately qualified and trained member of the study staff as allowed by local, state, and institutional guidance.

Following administration of study intervention(s), participants will be observed for the complete period/study by an appropriately qualified and trained member of the study staff.

Appropriate medication and other supportive measures for management of a medical emergency will be available in accordance with local guidelines and institutional guidelines.

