Natural log transformed AUCinf, AUClast and Cmax will be analyzed using a mixed effect model with sequence, period and treatment as fixed effects and participant within the sequence as a random effect. Estimates of the adjusted mean differences (Test-Reference) and corresponding 90% CIs will be obtained from the model. The adjusted mean differences and 90% CIs for the differences will be exponentiated to provide estimates of the ratio of adjusted geometric means (Test/Reference) and 90% CI for the ratios. Treatment A (etrasimod 2 mg clinical IR tablets under fasted conditions) will be the Reference treatment while Treatment B (etrasimod 2 mg mini tablets mixed with applesauce under fasted conditions), Treatment C (etrasimod 2 mg mini tablets mixed with chocolate pudding under fasted conditions), and Treatment D (etrasimod 2 mg mini tablets mixed with water under fasted conditions) will be the Test treatments.

Natural log transformed AUCinf, AUClast and Cmax will be analyzed using a mixed effect model with sequence and treatment as fixed effects and participant within the sequence as a random effect. Treatment A (etrasimod 2 mg clinical IR tablets under fasted conditions) will be the Reference treatment while Treatment E (etrasimod 2 mg mini tablets mixed with yogurt under fasted conditions) will be the Test treatment.

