Appendix 1. SAS Code for Analyses

An example of the PROC MIXED code is provided below:

For the primary objective – relative BA (B,C,D vs A):

proc mixed data=tab.pk; class seq period trt participant; model l&var=seq period trt/ ddfm=KR; random participant(seq) /subject=participant(seq); lsmeans trt; estimate 'B vs A' trt -1 1 0 0 0 /cl alpha=0.1; estimate 'C vs A' trt -1 0 1 0 0 /cl alpha=0.1; estimate 'D vs A' trt -1 0 0 1 0 /cl alpha=0.1;

> ods 'Estimates' out=est&var; ods 'Ismeans' out=Is&var; ods 'covparms' out=cov&var; ods 'tests3' out=tst&var;

run;

For the primary objective – relative BA (E vs A):

proc mixed data=tab.pk;

class seq trt participant; model l&var=seq trt/ ddfm=KR; random participant(seq) /subject=participant(seq); lsmeans trt; estimate 'E vs A' trt -1 0 0 0 1 /cl alpha=0.1;

ods 'Estimates' out=est&var; ods 'lsmeans' out=ls&var; ods 'covparms' out=cov&var; ods 'tests3' out=tst&var;

run;

/* Letter assignments for treatments (trt) within the estimate statement above are as follows Treatment A: Single oral dose of etrasimod 2 mg clinical IR tablet under fasted conditions (Reference)

Treatment B: Single oral dose of etrasimod 2 mg mini tablets mixed with applesauce under fasted conditions (Test 1)

Treatment C: Single oral dose of etrasimod 2 mg mini tablets mixed with chocolate pudding under fasted conditions (Test 2)

DMB02-GSOP-RF02 7.0 Statistical Analysis Plan Template 31-Jan-2022 PFIZER CONFIDENTIAL TMF Doc ID: 98.03 Page 17 of 20 Treatment D: Single oral dose of etrasimod 2 mg mini tablets mixed with water under fasted conditions (Test 3)

Treatment E: Single oral dose of etrasimod 2 mg mini tablets mixed with yogurt under fasted conditions (Test 4) */

Abbreviation	Term
%CV	coefficient of variation
AA	alopecia areata
AD	atopic dermatitis
AE	adverse event
AUC _{extrap} %	the percent of AUC _{inf} based on extrapolation
AUC _{inf}	area under the plasma concentration-time profile from time zero extrapolated to infinite time
AUC	
AUC _{last}	area under the plasma concentration-time profile from time zero to the time of the last quantifiable concentration
BA	bioavailability
BLQ	below the limit of quantitation
BP	blood pressure
CaPS	Clinical Data Interchange Standards Consortium and Pfizer Standards
CD	Crohn's Disease
CI	confidence interval
Clast	last quantifiable concentration
CL/F	apparent clearance after oral dose
C _{max}	maximum plasma concentration
CSR	clinical study report
ECG	electrocardiogram

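### The yogurt comparison (E/A) is primary, but E is given only in Period 5, so its ratio cannot be separated from a Period 5 effect, and the plan does not state the assumption this needs

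*Protocol*

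**What the plan says.** Protocol 4.1, with its four-sequence Table 2, describes the allocation as follows: those enrolled "are randomized in crossover design to receive Treatments A to D in Periods 1 to 4 with Treatment E being fixed in Period 5". SAP 2.3 repeats the layout.

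Protocol 3 lists the yogurt comparison among the four primary objectives, on the same footing as water, applesauce and pudding: "To estimate the rBA of the etrasimod 2 mg mini tablets mixed with yogurt compared to the etrasimod 2 mg clinical IR tablets".

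Protocol 9.3.3 and SAP 6.1 analyse B, C and D against A with sequence, period and treatment as fixed effects. E against A has its own model, without period: a "mixed effect model with sequence and treatment as fixed effects and participant within the sequence as a random effect".

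On numbers, Protocol 4.1 says: "Sixteen participants will be enrolled in Period 1 for a total of 12 evaluable participants to complete study".

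Conditions are well standardised. "Participants will be confined in the CRU for a total of at least 45 days" (4.1), and on dosing days, "following an overnight fast of at least 10 hours, participants will receive study intervention at approximately 0800 hours" (6.1.1). Meals and posture are controlled in 5.3.2 and 5.3.4.

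The first example call in SAP Appendix 1 reads "class seq period trt participant; model l&var=seq period trt/ ddfm=KR", with five-element contrasts such as "estimate 'B vs A' trt -1 1 0 0 0 /cl alpha=0.1". No restriction to Treatments A-D is shown.

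**The concern.** For B, C and D, randomisation balances the treatments over periods and the model adjusts for period. For E neither safeguard exists. By the schedule of activities, E is always dosed on study Day 37, while A is dosed on Day 1, 10, 19 or 28 depending on sequence. Anything that differs between the last period and the first four goes straight into E/A.

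Leaving period out of the E/A model is not a separate mistake; the design forces it. The gap is that the resulting assumption, that Period 5 equals the average of Periods 1-4, is nowhere stated. Protocol 4.2 gives no reason for placing E last. The SAP's model checks in 6.1 cover only residual normality and outliers. The 9-day washout deals with carryover, not with period effects.

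The study is for estimation, so the ratios and their 90% CIs are the product. As planned, all four are primary results of equal standing, although one interval makes no allowance for a period difference. The period test in the B/C/D model cannot help, because Periods 1-4 say nothing about a step at Period 5.

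**Working it through.** **Inputs.** Within-participant SDs 0.064 (lnAUCinf) and 0.0933 (lnCmax), Protocol 9.5. Participants: 16 enrolled, 12 evaluable, Protocol 4.1. Layout: Table 2. Half-life about 30 h and 9-day spacing, Protocol 4.1. The documents give no period effect, so every shift below is an assumption.

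**1. The plan's own figure.** Table 4 at a ratio of 100% follows from half-width h = t(0.95, df) × SD × √(2/n) × √(χ²(0.80, df)/df). With n = 12 and df = 3n − 6 = 30, for AUC: 1.697 × 0.064 × 0.4082 × √(36.25/30) = 0.0487. This gives 95.24% to 105.00%, width 9.75%, as printed. Cmax gives 93.14% to 107.36% (the printed width is 14.22%). With n = 16 the widths would be 8.26% and 12.05%, so Table 4 matches 12 participants.

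**2. Aliasing.** Write τ for treatment effects and π for period effects. With equal numbers per sequence, A falls equally in Periods 1-4, so

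estimate of ln(E/A) = (τE − τA) + π5 − (π1 + π2 + π3 + π4)/4.

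The design matrix for Table 2 (4 sequences × 4 participants × 5 periods = 80 rows; intercept, 4 sequence, 5 period and 5 treatment columns) has rank 11 of 15. One rank is lost because the Period 5 and Treatment E columns are identical. B−A, C−A and D−A are estimable; E−A is not.

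**3. Bias of the planned no-period model.** A Period 5 step of 0.05 gives 0.050, a factor of exp(0.05) = 1.051 on E/A. A drift of 0.01 per period gives 0.01 × (5 − 2.5) = 0.025. The second figure needs balanced sequences; with 12 evaluable split 4, 4, 2, 2 it is 0.0267. With the period term, B, C and D have no bias in either case.

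**4. Coverage of the nominal 90% CI for E/A.** Noncentral t, SE = SD × √(2/n). At n = 12 the SE is 0.0261 (AUC) and 0.0381 (Cmax). The ranges span df = n − 1 (only A and E in the model) to 4(n − 1) (all five treatments).

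| Assumed shift in E/A | AUC, n = 12 | Cmax, n = 12 |
|---|---|---|
| 0 | 90% | 90% |
| 0.01 | about 88% | about 89% |
| 0.02 | about 81% | about 86% |
| 0.025 (drift of 0.01 per period) | 75-77% | 83-84% |
| 0.03 | 69-71% | 80-81% |
| 0.05 | 40-44% | 64-66% |

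With all 16 evaluable, a 0.03 step gives 63-65% (AUC) and 77-78% (Cmax). A 0.05 shift is about as large as the AUC half-width in step 1.

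**5. Can a model rescue it?** A linear period term removes steady drift (bias 0.000) but none of a Period 5 step (bias still 0.050). Its SE is 0.520 SD against 0.408 SD, a ratio of 1.27.

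**6. Randomising E.** In a 5×5 Latin square with period as a class effect, the same step gives zero bias in E−A. The SE of any Test−A difference is 0.3542 SD with 16 participants (4,3,3,3,3), against √(2/16) = 0.3536 SD when balanced. With 12 (3,3,2,2,2) it is 0.410-0.411 SD, against √(2/12) = 0.408 SD.

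**7. Carryover.** Residual drug at 216 h is 2^(−216/30) = 0.68%.

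**8. Appendix 1 code.** If the first call is run on all five treatments, the B, C and D contrasts remain estimable, but `lsmeans trt` is non-estimable for all five treatments. With A-D data only, all four adjusted means are estimable.

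**The case against.** The fixed period is openly described, E/A has its own model visibly without period, and a statistical reader can infer the assumption. No hypothesis, margin or success rule depends on E/A. The documents report no period effect, and confinement, diet, posture, fasting and dosing time are all controlled, so a real step may be small or absent; at 0.01 the loss of coverage is only 1 to 2 points. The code is labelled as an example and the content of its dataset is not shown. A redesign needs an amendment with its approvals, and it gives up one benefit of the present layout: someone who leaves before Period 5 still contributes A to D.

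Much of this stands. The size of any bias is unknown, the larger shifts are illustrations, and the code point is minor. The effect on early leavers is a genuine trade-off. But disclosing the layout is not the same as stating the assumption it forces. Standardisation makes a period effect less likely without ruling it out. The absence of a test does not help either, because the estimate and interval are then all the study delivers.

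**Conclusion.** The concern holds and should be fixed. The aliasing is a property of Table 2 and depends on no assumption about the data; only its exact form, Period 5 minus the mean of Periods 1-4, requires balanced sequences. Whether E/A is actually biased is unknown. For shifts of 0.025 to 0.05 the bias itself is modest, about 2.5% to 5%. Coverage falls sharply because the assumed SDs are small. These coverage figures rest on the plan's SDs, the 12 evaluable participants and the assumed shifts. The B, C and D ratios and their intervals are unaffected, by the aliasing and by the code point alike. The code point costs only the supporting adjusted geometric means, and only if the call is run on all five treatments.

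**What to change.** **(a) Preferred.** Randomise all five treatments over the five periods that every participant already completes, and estimate all four ratios in one model with sequence, period and treatment. A single 5×5 Latin square suffices. It loses the exact carryover balance of Table 2, which matters little at 0.68% residual drug. A 10-sequence Williams-type pair of squares contains all 20 ordered treatment pairs and stays nearly balanced with 16 participants. The cost is a new randomisation schedule and an amendment with its approvals (Protocol 10.1.1), but no extra dose, visit or day. The SE rises by 0.2% with 16 participants and by under 1% with 12.

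**(b) If E must stay last.** Give the reason in Protocol 4.2. State in Protocol 9.3.3 and SAP 6.1 that E/A is not randomised with respect to period and assumes no difference between Period 5 and Periods 1-4. This takes about two sentences. A model with a linear period term may be added as a check on steady drift, at 1.27 times the SE, but it must not be presented as correcting a Period 5 step.

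**(c) If E stays fixed.** Restrict the B/C/D call in SAP Appendix 1 to Treatments A-D with four-element contrasts, so that the adjusted means are estimable. This is one data restriction and shorter contrasts.

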## 8.5. Pharmacokinetics

Blood samples of approximately 4 mL, to provide approximately 1.5 mL of plasma, will be collected for measurement of plasma concentrations of etrasimod as specified in the SoA. Instructions for the collection and handling of biological samples will be provided in the laboratory manual or by the sponsor. The actual date and time (24-hour clock time) of each sample will be recorded.

The actual times may change, but the number of samples will remain the same. All efforts will be made to obtain the samples at the exact nominal time relative to dosing. Collection of samples up to and including 10 hours after dose administration that are obtained within 10% of the nominal time relative to dosing (eg, within 6 minutes of a 60-minute sample) will not be captured as a protocol deviation, as long as the exact time of the collection is noted on the source document and the CRF. Collection of samples more than 10 hours after dose administration that are obtained  $\leq 1$  hour away from the nominal time relative to dosing will not be captured as a protocol deviation, as long as the exact time of the collection is noted on the source document and the CRF. This protocol deviation window does not apply to samples to be collected more than 10 hours after dose administration at outpatient/follow-up visits with visit windows.

Samples will be used to evaluate the PK of etrasimod. Samples collected for analyses of etrasimod plasma concentration may also be used to evaluate safety or efficacy aspects related to concerns arising during or after the study, for protein binding, metabolite identification and/or evaluation of the bioanalytical method, or for other internal exploratory purposes. The exploratory results may not be reported in the CSR.

Genetic analyses will not be performed on these PK samples.

Samples collected for measurement of plasma concentrations of etrasimod will be analyzed using a validated analytical method in compliance with applicable SOPs.

The PK samples must be processed and shipped as indicated in the instructions provided to the investigator site to maintain sample integrity. Any deviations from the PK sample handling procedure (eg, sample collection and processing steps, interim storage or shipping conditions), including any actions taken, must be documented and reported to the sponsor. On a case-by-case basis, the sponsor may make a determination as to whether sample integrity has been compromised.

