Any changes in the timing or addition of time points for any planned study assessments must be documented and approved by the relevant study team member and then archived in the sponsor and site study files, but will not constitute a protocol deviation. The IRB/EC will be informed of any safety issues that require alteration of the safety monitoring scheme or amendment of the ICD.

Additional blood samples of approximately 0.5 mL using a micro sampling device (Tasso) will be collected, to provide approximately 0.25 mL serum into appropriately labeled tubes for measurement of etrasimod at selected timepoints as specified in the SoA.

The "Tasso device" is an integrated capillary blood collection device. This part of the study is designed to validate etrasimod PK concentrations in capillary blood collected using the Tasso device against PK samples collected from traditional venous blood samples. Findings from the validation may enable patient-centric blood sampling using this innovative device in future etrasimod pediatric clinical studies.

Blood samples from capillary blood vessels, collected using the Tasso device, should be timed as close as possible to the collection of etrasimod blood samples. The Tasso device should be attached to the upper arm. Details for collection and handling of the samples will be provided in the laboratory manual.

The blood samples collected using Tasso device will be used for internal exploratory purposes for comparing the etrasimod concentrations between venous and capillary blood.

The results from this comparison will be documented in a separate internal bioanalytical report and will not be included in the CSR.

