# 9.3.3. Pharmacokinetic Analyses

Plasma PK parameters of etrasimod will be derived (as data permit) from the concentration-time data using standard noncompartmental methods as outlined in the Table 3 below. Actual PK sampling times will be used in the derivation of PK parameters. In the case that actual PK sampling times are not available, nominal PK sampling time will be used in the derivation of PK parameters.

Parameter	Definition	Method of Determination
AUC inf	Area under the concentration-time curve from time zero extrapolated to infinity	AUC last + ( $C_{last}$ */ $k_{el}$ ), where $C_{last}$ * is the predicted plasma concentration at the last quantifiable time point from the log-linear regression analysis
AUC last	Area under the plasma concentration-time profile from time zero to the time of the last quantifiable concentration (C last )	Linear/Log trapezoidal method.
C max	Maximum observed concentration	Observed directly from data
T max	Time for C max	Observed directly from data as time of first occurrence
t 1/2	Terminal half-life	$Log_e(2)/k_{el}$ , where $k_{el}$ is the terminal phase rate constant calculated by a linear regression of the loglinear

 Table 3.
 Plasma Etrasimod PK Parameters Definitions

Parameter	Definition         Method of Determination	
		concentration-time curve. Only those data points judged to describe the terminal loglinear decline will be used in the regression.
CL/F	Apparent clearance	Dose/AUC inf
V z /F	Apparent volume of distribution	$Dose/(AUC_{inf} \bullet k_{el})$

 Table 3.
 Plasma Etrasimod PK Parameters Definitions

PK parameters will be summarized descriptively by treatment, in accordance with Pfizer data standards. Plasma concentrations will be listed and summarized descriptively by nominal PK sampling time and treatment. Individual participant and median profiles of the plasma concentration-time data will be plotted by treatment using actual and nominal times, respectively. Median profiles will be presented on both linear-linear and log-linear scales.

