6.3.2. Etrasimod micro sampling concentration

The micro sampling will be performed in this study, but the results of analyzing this data will not be included in the CSR. Instead, a separate internal bioanalytical report will be issued to document data and conclusions from this analysis. However, *etrasimod concentration at sampling time points*, C_{max} and AUC_{0-24} from paired samples obtained via micro sampling and venous sampling will be compared. Individual participant differences and % differences

DMB02-GSOP-RF02 7.0 Statistical Analysis Plan Template 31-Jan-2022 PFIZER CONFIDENTIAL TMF Doc ID: 98.03 Page 14 of 20 of concentrations by PK sampling time, C_{max} and AUC_{0-24} will be listed and summarized descriptively.

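### The capillary sample always follows the venous one and pairs are not aligned in time, so the exploratory 1 h comparison can be biased upward by about 1% per minute of delay

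*Protocol*

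**What the plan says.** Protocol 4.1 (Overall Design) and the Schedule of Activities pair eight capillary samples with venous samples under Treatment A: predose and 1, 2, 4, 6, 8, 12 and 24 h. The order is fixed: "Micro PK sampling occurs after PK blood sampling, and taken from the other arm".

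Protocol 8.5 (Pharmacokinetics) governs the timing. Capillary draws "should be timed as close as possible to the collection of etrasimod blood samples", with no limit in minutes. The no-deviation window, 10% of nominal time up to 10 h and so 6 minutes at 1 h, is set around the nominal time and not between the two draws. Actual times are kept: "The actual date and time (24-hour clock time) of each sample will be recorded". That sentence stands in the venous paragraph and is not repeated in the capillary one.

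On analysis, SAP 6.3.2 (like Protocol 9.3.5) says that concentrations, Cmax and AUC0-24 "from paired samples obtained via micro sampling and venous sampling will be compared". Individual differences and percentage differences are listed and summarised, the concentrations by sampling time. Protocol 9.3.3 states "Actual PK sampling times will be used in the derivation of PK parameters". Neither document extends this to the pointwise concentration differences.

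**The concern.** Because the order never changes, the delay has the same sign in every pair, and averaging over participants cannot remove it. While concentration is rising, a later sample reads higher. An excess produced only by elapsed time can therefore look like a difference between capillary and venous measurement.

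The stated exploratory objective (Protocol 3) is to validate capillary against venous measurement, and Protocol 4.2.3 links the result to blood sampling in a future paediatric study. No agreement limit is given, so readers of the internal report will judge the percentage differences directly.

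**Working it through.** The plan states no precision, margin or expected difference for this comparison, so there is no figure of its own to reproduce. The check sizes the timing effect when the two methods agree exactly.

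**Inputs from the documents.** Median Tmax 4 h for the fasted IR tablet and half-life about 30 h (Protocol 2.2.4.1); pair times and draw order (Protocol 4.1); 16 enrolled, 12 evaluable (Protocol 4.1).

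**Assumptions.** One-compartment oral model without absorption lag, and delays of 1 to 15 minutes. The documents give neither the model nor the delay.

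**Model.** C(t) is proportional to exp(−ke·t) − exp(−ka·t), with ke = ln 2/30 = 0.0231 per h. Solving ln(ka/ke)/(ka − ke) = 4 gives ka = 0.953 per h.

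**Bias.** C(t + d)/C(t) − 1 for delay d. At 1 h with d = 5 min:
- C(1) = 0.9772 − 0.3856 = 0.5916
- C(1.083) = 0.9753 − 0.3561 = 0.6191
- 0.6191/0.5916 − 1 = +4.7%

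| Delay | 1 h | 2 h | 4 h | 6 h | 8 to 24 h |
|---|---|---|---|---|---|
| 1 min | +0.96% | +0.25% | 0.00% | −0.03% | −0.04% |
| 2 min | +1.91% | +0.49% | 0.00% | −0.07% | −0.08% |
| 5 min | +4.66% | +1.18% | −0.01% | −0.16% | −0.19% |
| 10 min | +8.94% | +2.25% | −0.03% | −0.33% | −0.38% |
| 15 min | +12.87% | +3.23% | −0.06% | −0.50% | −0.56% to −0.58% |

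The 2 h bias is about a quarter of the 1 h bias (1.18/4.66 = 0.25).

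**Sensitivity, 5-minute delay at 1 h.** Without absorption lag: +1.7% (Tmax 2 h), +3.5% (3 h), +6.0% (6 h). With an assumed 0.5 h lag: +5.5% (Tmax 2 h), +11.7% (4 h), +13.7% (6 h). The sign is positive throughout.

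**Cmax and AUC0-24.** For delays up to 15 minutes in the base case, Cmax changes by less than 0.1%. AUC0-24 changes by at most +0.21% on nominal times or −0.13% on actual times.

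**Scale against noise.** The 90% CI half-width of the mean 1 h difference is exp(t(0.95, n−1)·s/√n) − 1. For an assumed SD s of paired log differences of 0.10 to 0.20, this is 4.5% to 9.2% (n = 16) or 5.3% to 10.9% (n = 12).

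**Effect of interpolation.** Take the venous value on the straight line from C(1) = 0.5916 to C(2) = 0.8062.
- 5 min: 0.5916 + 0.2146 × 5/60 = 0.6095; 0.6191/0.6095 − 1 = +1.6%, down from +4.7%
- 10 min: 0.5916 + 0.2146 × 10/60 = 0.6274; C(1.167) = 0.6444; 0.6444/0.6274 − 1 = +2.7%, down from +8.9%

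A residual remains because the curve is concave between 1 h and 2 h, so the line lies below it.

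**The case against.** The strongest reply is that Protocol 8.5 already tells staff to keep the two draws close together. If they manage 1 to 2 minutes, the bias is 1% to 2%, well inside the sampling noise above. The laboratory manual, which is not available here, may also set a limit. This stands: the size depends on a delay that the documents do not give.

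A reader might infer from the 10% window that the two draws may sit at its opposite ends, 12 minutes apart at 1 h. The documents do not support that reading, because such a pair would go against the instruction on close timing.

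A reader might also infer that actual times are ignored altogether. They are not: Protocol 9.3.3 and SAP 5.3.1 use them to derive PK parameters, which covers Cmax and AUC0-24. Only the pointwise differences lack such a rule, and their use of nominal time is inferred from pairing by time point, since neither section writes the word. SAP 5.3.1 further allows a concentration with a worrying time deviation to be set to missing in summary tables. It gives no threshold, so it is unlikely to catch a lag of a few minutes.

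Finally, results are shown time by time. A timing artefact would appear at 1 h, weakly at 2 h, and then vanish, whereas a constant proportional device effect would persist at every postdose point. That is a real safeguard for a reader who looks for the pattern. It does not help if a genuine capillary-venous difference is itself confined to the early samples.

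**Conclusion.** The point holds as a minor one. With a fixed draw order, no stated maximum gap and no time alignment, the 1 h concentration comparison can be biased upward by about 1% per minute of delay. This rests on the assumed one-compartment model with Tmax 4 h and half-life 30 h; at a 5-minute delay, the alternatives tried range from +1.7% to +13.7%. The bias is small at 2 h and negligible from 4 h on.

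It would be too strong to say that the 1 h excess will be taken for a device effect, or that the capillary validation as a whole is compromised. The delay is unknown, one of seven postdose points is materially affected, and Cmax and AUC0-24 are practically unchanged. The comparison is exploratory and descriptive, and both documents keep it out of the CSR. No primary or secondary result changes.

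**What to change.** In Protocol 9.3.5 and SAP 6.3.2:

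- Keep the raw differences and percentage differences. Beside them, present the same quantities against the venous concentration interpolated to the recorded actual capillary time, using the linear/log rule already specified for AUClast. Venous sampling continues to 48 h and beyond, so the 24 h pair is bracketed too.
- List the venous-capillary gap in minutes for each pair, and confirm that the recording rule in Protocol 8.5 covers capillary samples.
- State that interpolation between the 1 h and 2 h samples reduces the 1 h bias but does not remove it (modelled: 4.7% to 1.6% at 5 minutes, 8.9% to 2.7% at 10 minutes).
- State that an excess confined to 1 to 2 h will be interpreted as possibly due to timing.

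The cost is a little more programming on times that should already be recorded, with no extra samples. The downside is that the aligned differences depend on interpolation at the early points, where sampling is sparse relative to the curvature; showing the raw values alongside keeps that visible. If site instructions can still be changed, a stated maximum gap or an alternating draw order would act on the cause, but the analysis change does not depend on it.
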